|------------------------------------|---|

| | |
|--|---|
| | 
The goal for the IP is that the mean \log_{10} reduction of all four primary objectives meets the following criteria:
 
 1. The lower limit of the 95% confidence interval (two-sided) of mean log reduction at 30 seconds will be greater than or equal to 2 for the abdomen. 2. The lower limit of the 95% confidence interval (two-sided) of mean log reduction at 30 seconds will be greater than or equal to 3 for the groin. 3. The lower limit of the 95% confidence interval (two-sided) of mean log reduction at 6 hours will be greater than or equal to 2 for the abdomen. 4. The lower limit of the 95% confidence interval (two-sided) of mean log reduction at 6 hours will be greater than or equal to 3 for the groin 
The HC testing requirements will only be considered met when and only when all four primary objectives pass HC analysis acceptance criteria. No multiplicity adjustment is required.
 
The RS should meet the same efficacy standards as the IP.
 
HC Exploratory Analysis: 1) The following descriptive statistics for \log_{10} CFU/cm² reductions will be computed for the IP and RS, grouped by anatomical site and each post application sampling for the 10 minute time point: mean, median, standard deviation, minimum, maximum, and count. The 95% confidence intervals (two-sided) will be calculated for the observed log reductions for the IP and RS at the 10 minute time point on each anatomical area.
 
2) \log_{10} CFU/cm² reductions at 30 seconds, 10 minutes, and 6 hours on the abdomen and the groin for the IP will be compared to the RS using two-sample t-test.
 
FDA Efficacy Analyses
 
FDA Primary Analysis: A linear regression model for each body site (abdomen and groin) will be used for primary analysis of efficacy at 10 minutes. In the model, the response is the post-product application bacterial counts at 10 minutes and predictors are the study products as a fixed effect and the pre-product application bacterial loads as a covariate. The ATE corrected for pre-product application bacterial loads will be estimated from the model and compared to both non-inferiority and superiority criteria.
 
The FDA testing requirements for the primary analysis will only be considered met when and only when all four primary objectives (10 minutes for both abdomen and groin) pass FDA analysis acceptance criteria, no multiplicity adjustment is required.
 
To evaluate the persistent antimicrobial properties of a single Swabstick impregnated with 2% (w/v) chlorhexidine gluconate in 70% (v/v) isopropyl alcohol, \log_{10} bacterial counts at 6 hours post product application for each product application site will be converted to a binary (yes or no) success measure with success defined as having skin flora counts that are less than or equal to the baseline skin flora counts. Responder rates at 6 hours post product application will be summarized descriptively for each
 |

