2.2.2 Exploratory Objectives

The first exploratory objective is to evaluate the \log_{10} CFU/ cm^2 reductions from baseline for the IP and RS at each anatomical site, abdomen and groin, at 10 minutes post-product application. The second exploratory objective is to determine if the 30-second, 10 minutes and 6 hour \log_{10} CFU/ cm^2 reductions on the abdomen and groin for the IP are not statistically worse than those for 60% v/v 1-propanol post product application.

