3.3 Product Application Allocation and Methods to Reduce Bias

3.3.1 Randomization

The randomization scheme for the study will be provided by the Sponsor. A sufficient number of subjects will be recruited and newly randomized to meet the minimum number of evaluable product application sites per study product arm, preserving the randomization assignment. The number of evaluable product application sites per study product arm per anatomical area will be monitored to determine additional subject enrollment and randomization to meet the required evaluable sample size. Subjects who fail to meet Product Application Day baselines will not be replaced. Additional subjects will be randomized to account for product application day failures.

Subjects will be randomized to study product arms using the following block design:

Study Product Balance

Each subject will receive two different study products, one on the right side of the body and one on the left. Therefore, there are six possible study product combinations: A-B, A-C, A-D, B-C, B-D and C-D.

A minimum of 516 evaluable subjects will be required to achieve a total of a minimum of 192 evaluable product application sites for groin and abdominal regions for 60% (v/v) 1-propanol (RS) and 280 evaluable product application sites for groin and abdominal regions for the other three study product arms. Due to the imbalance of the sample size between RS and other products, RS cannot be blinded. Assuming the treatment code for RS is B and all the other three products are either A, C or D, within each small block [i.e., every 129 (516/4) evaluable subjects randomized], number of subjects who receive each product combination is shown below. With 4 blocks in total (i.e., 516 evaluable subjects), the minimum of 192 evaluable product application sites for groin and abdominal regions for 60% (v/v) 1-propanol (RS) and 280 evaluable product application sites for groin and abdominal regions for the other three study product arms can be achieved.

| Product Combination | No. of Subjects in Each Block |
|---------------------|-------------------------------|
| A-B | 16 |
| A-C | 27 |
| A-D | 27 |
| B-C | 16 |
| B-D | 16 |
| C-D | 27 |
| Total | 129 |

Left/Right Balance

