13.0 STATISTICAL METHODS

13.1 Sample Size Determination

To evaluate the primary objective for HC analysis a sample size of at least 192 evaluable sites per study product arm (IP or RS) per body site can achieve > 95% power to pass HC analysis acceptance criteria for all four objectives using one-sample t-test (two-sided), with the following assumptions.

- Two-sided test Type I error (α): 0.05
- Standard deviation and mean log reduction:

| Time Point | Study Product | Standard Deviation | | Log Reduction | |
|------------|---------------|--------------------|-------|---------------|-------|
| | | Abdomen | Groin | Abdomen | Groin |
| 30 Seconds | IP | 1.14 | 1.43 | 3.47 | 3.38 |
| 6 hours | IP | 1.22 | 1.24 | 3.43 | 3.50 |

To evaluate the primary and secondary objectives for the US FDA analysis a sample size of 280 evaluable sites per study product arm (IP, AC or NC) per body site can achieve > 95% power to demonstrate the non-inferiority of the Investigational Product (IP) as compared to the Active Control (AC) and the superiority of the IP as compared to the negative control (NC) in antimicrobial effect at 30-second (abdomen only) and 10-minute (abdomen and groin) post-product application time point for all six objectives, with the following assumptions:

- Two-sided test Type I error (α): 0.05
- Average Treatment Effect in \log_{10} CFU/cm²:

| Average Treatment Effect | Abdomen | Groin |
|--------------------------|---------|-------|
| IP – AC | 0.06 | 0.10 |
| NC – IP | 1.58 | 2.31 |

- Standard deviation for each treatment effect for Abdomen: 1.05 \log_{10}
- Standard deviation for each treatment effect for Groin: 1.2 \log_{10}

The overall power to pass both HC analysis and US FDA analysis acceptance criteria is > 90%.

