13.5.2 HC Exploratory Analyses

1. The following descriptive statistics for \log_{10} CFU/cm² reductions will be computed for the IP and RS, grouped by anatomical site and each post application sampling for the 10 minute time point: mean, median, standard deviation, minimum, maximum, and count. The 95% confidence intervals (two-sided) will be calculated for the observed log reductions for the IP and RS at the 10 minute time point on each anatomical area using one-sample t-test (two-sided).
2. \log_{10} CFU/cm² reductions at 30 seconds, 10 minutes, and 6 hours on the abdomen and the groin for the IP will be compared to the RS using two-sample t-test (two sided).

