2.2.2.2 Exploratory Objective

- To evaluate the \log_{10} CFU/cm² reductions from baseline for the IP and RS at each anatomical site, abdomen and groin, at 10 minutes post-product application.
- To determine if the 30-second, 10 minutes and 6 hour \log_{10} CFU/cm² reductions on the abdomen and groin for the IP are not statistically worse than those for 60% v/v 1-propanol post-product application.

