6.2.1.3 Exploratory Analysis

The same analysis as described in Section [6.2.1.2](#) will be performed for log reduction at the 10 minute time point on each anatomical area for the IP and RS using one-sample t-test (two-sided) (cf. Table [A.2.5](#)).

\log_{10} CFU/cm² reductions at 30 seconds, 10 minutes, and 6 hours on the abdomen and the groin for the IP will be compared to the RS using two-sample t-test (two-sided). Difference in log reduction along with 95% confidence interval (CI) at each post application sampling time point will be compared to zero. If 95% CI contains zero, the conclusion is no significant difference in log reduction between IP and RS. If 95% CI does not contain zero, the conclusion is significant difference in log reduction exists and the direction of the difference will be indicated (cf. Table [A.2.6](#)).

A graph for the log reduction at each post application sampling time point with 95% confidence interval will be provided (cf. Figure C.1.1 created based on the simulated data).

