	mITT Responder Rate 6 Hours	n	n	n	n
	PP Responder Rate 6 Hours	n	n	n	n
	mITT Product Weight	n	n	n	n
	PP Product Weight	n	n	n	n

A.2 HC Analysis

Table A.2.1: mITT/PP - Summary Statistics for HC Analysis - Log CFU

Body Location	Product	Time Point	Count	Mean	Median	SD	Range (Min-Max)
Abdomen/Groin	IP/RS	Baseline	n	x.xx	x.xx	x.xx	x.xx - x.xx
		30 Seconds	n	x.xx	x.xx	x.xx	x.xx - x.xx
		10 Minutes	n	x.xx	x.xx	x.xx	x.xx - x.xx
		6 Hours	n	x.xx	x.xx	x.xx	x.xx - x.xx

Table A.2.2: mITT/PP - Summary Statistics for HC Analysis - Log Reduction

Body Location	Product	Time Point	Count	Mean	Median	SD	Range (Min-Max)
Abdomen/Groin	IP/RS	30 Seconds	n	x.xx	x.xx	x.xx	x.xx - x.xx
		10 Minutes	n	x.xx	x.xx	x.xx	x.xx - x.xx
		6 Hours	n	x.xx	x.xx	x.xx	x.xx - x.xx

Table A.2.3: mITT/PP - Summary Statistics for HC Analysis - Product Weight

Body Location	Product	Count	Mean	Median	SD	Range (Min-Max)
Abdomen/Groin	IP/RS	n	x.xx	x.xx	x.xx	x.xx - x.xx

Table A.2.4: mITT/PP - Analysis Results for HC Analysis - Log Reduction at 30 Seconds and 6 Hours

Body Location	Product	Time Point	Count	Mean Log Reduction (95% CI)	Met Criteria
Abdomen/Groin	IP/RS	30 Seconds	n	x.xx (x.xx, x.xx)	Yes/No
		6 Hours	n	x.xx (x.xx, x.xx)	Yes/No

Table A.2.5: mITT/PP - Analysis Results for for HC Analysis - Log Reduction at 10 Minutes

Body Location	Product	Time Point	Count	Mean Log Reduction (95% CI)
Abdomen/Groin	IP/RS	10 Minutes	n	x.xx (x.xx, x.xx)

Table A.2.6: mITT/PP - Analysis Results for for HC Analysis - Difference in Log Reduction

Body Location	Contrast	Time Point	Difference in Log Reduction (95% CI)	Conclusion
Abdomen/Groin	IP-RS	30 Seconds	x.xx (x.xx, x.xx)	Sign. Diff/No Sign. Diff
Abdomen/Groin	IP-RS	10 Minutes	x.xx (x.xx, x.xx)	Sign. Diff/No Sign. Diff
Abdomen/Groin	IP-RS	6 Hours	x.xx (x.xx, x.xx)	Sign. Diff/No Sign. Diff

A.3 FDA Analysis

Table A.3.1: mITT/PP - Summary Statistics for FDA Analysis - Log CFU

Body Location	Product	Time Point	Count	Mean	Median	SD	Range (Min-Max)
Abdomen/Groin	IP/AC/NC	Baseline	n	x.xx	x.xx	x.xx	x.xx - x.xx
		30 Seconds	n	x.xx	x.xx	x.xx	x.xx - x.xx
		10 Minutes	n	x.xx	x.xx	x.xx	x.xx - x.xx
		6 Hours	n	x.xx	x.xx	x.xx	x.xx - x.xx

Table A.3.2: mITT/PP - Summary Statistics for FDA Analysis - Log Reduction

Body Location	Product	Time Point	Count	Mean	Median	SD	Range (Min-Max)
Abdomen/Groin	IP/AC/NC	30 Seconds	n	x.xx	x.xx	x.xx	x.xx - x.xx
		10 Minutes	n	x.xx	x.xx	x.xx	x.xx - x.xx
		6 Hours	n	x.xx	x.xx	x.xx	x.xx - x.xx

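### The Health Canada exploratory comparison with 1-propanol asks whether the IP is not worse but only tests the difference against zero, so a null result is not evidence of comparability (minor)

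*SAP*

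**What the plan says.** The exploratory objective in SAP 2.2.2.2 is to find out whether the log reductions at 30 seconds, 10 minutes and 6 hours "on the abdomen and groin for the IP are not statistically worse than those for 60% v/v 1-propanol". Protocol 2.2.2 and the protocol Summary set the same objective.

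The protocol gives one analysis for it. In the Summary, the log reductions "for the IP will be compared to the RS using two-sample t-test", and Protocol 13.5.2 adds that the test is two-sided. SAP 6.2.1.3 supplies the decision rule, which compares the 95% CI of the difference with zero: "If 95% CI contains zero, the conclusion is no significant difference in log reduction between IP and RS". If zero lies outside the interval, a significant difference is declared and its direction given. Table A.2.6 ("HC Analysis - Difference in Log Reduction") prints the IP-RS difference with its 95% CI and a conclusion that is either *Sign. Diff* or *No Sign. Diff*.

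No IP-RS margin is given anywhere. The Health Canada sample size calculation covers the one-sample criteria and does not size this comparison. On the design, Protocol 3.3.1 states: "Each subject will receive two different study products, one on the right side of the body and one on the left".

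**The concern.** An interval that contains zero shows that no difference was detected. It does not show that the IP is not worse, and the less precise the estimate, the easier the rule is to satisfy. The objective is phrased as something to be determined, so a report could present *No Sign. Diff* as a positive answer while a deficit of 0.2 to 0.3 log10 remained compatible with the data. For the FDA comparison with the active control, the same plan judges the interval against a stated 0.5 log10 margin. For the RS it has none.

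A second, smaller point concerns the test itself. It treats IP and RS sites as coming from different people, although some subjects receive both products, and it leaves out the baseline count that the FDA regression uses as a covariate.

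**Working it through.** **Inputs.** 280 IP sites and 192 RS sites per body region (Protocol 4.0 and 13.1). The SDs of IP log reduction are 1.14 (abdomen) and 1.43 (groin) at 30 seconds, and 1.22 and 1.24 at 6 hours (Protocol 13.1, SAP Table 2). The documents give no RS SD, no 10-minute SD for log reduction and no within-subject correlation. These are varied or left out below.

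**The plan's own figure.** For 192 sites the plan states more than 95% power on all four IP criteria. The weakest is groin at 30 seconds: (3.38 - 3)/(1.43/√192) = 3.68, which gives power 0.956 from the noncentral t. The others are above 0.999, so joint power is 0.956 and the claim reproduces. It concerns the IP alone and says nothing about IP-RS.

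**Precision of IP-RS.** Assume first that the RS SD equals the IP SD. Then SE = SD × √(1/280 + 1/192) = SD × 0.0937, and the half-width is 1.96 × SE. An interval that only just contains zero has its lower limit at -2 × half-width. For a true deficit d, P(CI contains 0) = Φ(1.96 - d/SE) - Φ(-1.96 - d/SE).

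| Cell | SD | SE | Half-width | Lowest lower limit | d = 0.20 | d = 0.30 | d = 0.50 |
|---|---|---|---|---|---|---|---|
| Abdomen 30 s | 1.14 | 0.107 | 0.209 | -0.419 | 0.535 | 0.198 | 0.003 |
| Abdomen 6 h | 1.22 | 0.114 | 0.224 | -0.448 | 0.583 | 0.253 | 0.008 |
| Groin 6 h | 1.24 | 0.116 | 0.228 | -0.455 | 0.594 | 0.267 | 0.010 |
| Groin 30 s | 1.43 | 0.134 | 0.263 | -0.525 | 0.680 | 0.390 | 0.038 |

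**If the RS SD differs.** With RS SD = f × IP SD, SE = √(SD²/280 + (f × SD)²/192).

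- f = 0.8: P(CI contains 0) is 0.114 to 0.286 at d = 0.30 and at most 0.012 at d = 0.50.
- f = 1.25: it is 0.318 to 0.508 at d = 0.30 and 0.018 to 0.102 at d = 0.50. The lowest lower limit becomes -0.48 (SD 1.14) to -0.61 (SD 1.43).

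**Shared subjects.** Each block in Protocol 3.3.1 has 16 subjects for every pairing that includes the RS, and there are four blocks. So 16 × 4 = 64 planned subjects carry both IP and RS, which is 64/192 = one third of the RS sites. With within-subject correlation ρ, the true variance of the difference in means is SD² × (1/280 + 1/192 - 2 × 64 × ρ/(280 × 192)). The t-test omits the last term.

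| ρ (assumed) | Nominal SE / true SE | Actual coverage | Model SE / t-test SE |
|---|---|---|---|
| -0.2 | 0.974 | 94.4% | 1.023 |
| 0 | 1.000 | 95.0% | 1.000 |
| 0.1 | 1.014 | 95.3% | 0.985 |
| 0.3 | 1.043 | 95.9% | 0.946 |
| 0.5 | 1.076 | 96.5% | 0.885 |

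The last column is generalised least squares on the IP and RS sites only (64 pairs, 216 IP-only sites, 128 RS-only sites, equal variances), before any effect of the baseline covariate. The evaluable number of shared subjects may differ from 64. At ρ = 0.3, 40 to 80 of them give a nominal/true ratio of 1.026 to 1.055.

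**The case against.** The strongest reply is that the objective, read literally, is answered. It does not say non-inferior. SAP 6.2.1.3 gives the only rule, and under that rule statistically worse means an interval wholly below zero. The authors write a margin and name non-inferiority when they intend it, as they do for the active control. The label *No Sign. Diff* is accurate as a label, and Table A.2.6 prints the difference and CI beside it, so a reader can see the lower limit. The objective is exploratory, and the RS is also judged against the same absolute limits as the IP.

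Most of this stands. A reader might infer that the plan claims non-inferiority to 1-propanol from a null result, but neither document makes that claim. A reader might also infer that a large deficit could pass unnoticed. At the planned sizes a true 0.50 log10 deficit would give an interval containing zero in 0.3 to 3.8% of trials with equal SDs, and in at most about 10% if the RS SD is 1.25 times the IP's. What remains is that the objective's wording invites a positive conclusion that the rule cannot supply, and nothing in the SAP rules that conclusion out.

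On the shared subjects, Protocol 4.0 describes the four application sites on a subject as independent. That is an assumption, and the paired allocation gives reason to doubt it. Its effect is small, though. It would be wrong to infer that the shared subjects invalidate the test: a positive correlation makes the interval slightly too wide, which is conservative.

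**Conclusion.** The concern holds as a minor point. The rule supports the statement that the IP was not significantly worse. It does not support a statement that the IP is comparable to, or no worse than, 1-propanol.

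If the RS SD equals the IP SD, the interval contains zero in 54 to 68% of trials at a true 0.20 log10 deficit (rounded from 0.535 and 0.680) and in 20 to 39% at 0.30. Such an interval reaches no lower than about -0.42 to -0.53 log10. This is not an absolute bound, because it moves to -0.48 to -0.61 if the RS SD is 1.25 times the IP's. The figures cover 30 seconds and 6 hours; 10 minutes could not be computed for lack of an SD.

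Ignoring the shared subjects inflates the nominal SE by about 1 to 8% for ρ between 0.1 and 0.5. If ρ is negative, the error is small and in the other direction. No Health Canada or FDA success decision changes, since SAP 2.5 rests those on the primary and gated secondary criteria alone.

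**What to change.** 1. **Interpretation.** State in SAP 6.2.1.3 and under Table A.2.6 that *No Sign. Diff* will not be read as not worse or as non-inferior, and that the IP-RS difference with its 95% CI is reported as an estimate. State also that a positive difference in log reduction favours the IP.
2. **Analysis.** For each body region and time point, estimate IP-RS from a model of log reduction with product, baseline log10 count as covariate and a subject effect, fitted to the IP and RS sites. Keeping log reduction as the response preserves the sign in Table A.2.6. With baseline as a covariate, modelling log count would give the same product difference with the sign reversed. A within-subject residual correlation in place of a random effect would also allow ρ to be negative.

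A margin is optional. If the sponsor wants a not-worse conclusion, an IP-RS margin needs its own justification before database lock. The 0.5 log10 margin set for the active control should not be carried over by default.

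**Cost.** No new data are needed. The first change is SAP text only, and it removes the main problem even if the t-test is kept. The second adds a little analysis work. The protocol names the t-test and words the objective in 2.2.2, 13.5.2 and the Summary, so changing either there requires an amendment with IRB/EC approval under Protocol 15.4.

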6.2.2 FDA Analysis

6.2.2.1 Summary Statistics

The following descriptive statistics for \log_{10} CFU/cm² at each time point (baseline, 30 seconds, 10 minutes and 6 hours) and \log_{10} CFU/cm² reductions at each post application sampling time point (30 seconds, 10 minutes and 6 hours) will be computed for the IP, AC and NC, grouped by anatomical site: mean, median, standard deviation, minimum, maximum, and count (cf. Tables A.3.1 and A.3.2).

Responder rates at 6 hours post-product application will be summarized descriptively for each product (IP, AC and NC) on each body site. No inferential analysis will be performed on the responder rates at 6 hours post-product application (cf. Table A.3.3).

The following descriptive statistics for product weight will be computed for the IP, AC and NC, grouped by anatomical site: mean, median, standard deviation, minimum, maximum, and count (cf. Table A.3.4).

6.2.2.2 Primary Analysis

A linear regression model for each body site (abdomen or groin) will be used for primary analysis of efficacy at 10 minutes. In the model, the response is the post-product application bacterial counts at 10 minutes and predictors are the study products (IP, AC or NC) as a fixed effect and the pre-product application bacterial loads as a covariate. The average treatment effect (ATE) corrected for pre-product application bacterial loads will be estimated from the model and compared to both non-inferiority and superiority criteria (cf. Table A.3.5).

For assessment of the four primary objectives (i.e., immediate activity at 10 minutes post application on the abdomen and groin for non-inferiority and superiority):

- A non-inferiority criterion with a 0.5 \log_{10} margin will be implemented for ATE of the IP compared to the AC (i.e., if the upper two-sided 95% confidence bound of the post-product application bacterial load corrected for pre-product application bacterial load of the IP-AC is less than 0.5 \log_{10} , the non-inferiority criterion is met).
- A 1.2 \log_{10} superiority criterion will be implemented for the ATE of the IP compared to the NC (i.e., if the lower two-sided 95% confidence bound of the post-product application bacterial load corrected for pre-product application bacterial load of the NC-IP is greater than 1.2 \log_{10} , the superiority criterion is met).

A graph showing the ATE with 95% confidence intervals for post-product log CFU at 10 minutes correcting for pre-product application will be provided for each contrast (cf. Figure C.2.1 created based on the simulated data).

